8.4.1. Adverse Events

Adverse events (AEs) will be coded using MedDRA Version 24.1 or higher. In the event of a missing/incomplete start or stop date associated with an adverse event, only the treatment-

emergence will be imputed using the algorithm described in Appendix B. Dates will not be imputed.

A TEAE is defined as an AE with onset at or after the start of IP, or any worsening of a preexisting medical condition/AE with onset at or after the start of IP and throughout the study. A non-TEAE is any adverse event that starts prior to IP. The term IP includes both SAGE-324 and placebo.

An overall adverse event summary table will be presented for TEAEs and will include the number and percent of participants experiencing at least one:

- TEAE
- Maximum severity of TEAE (mild TEAE, moderate TEAE, severe TEAE)
- TEAE leading to study treatment discontinuation
- TEAE leading to study discontinuation
- Serious TEAE
- Serious TEAE leading to study treatment discontinuation
- Serious TEAE leading to study discontinuation
- TEAE resulting in death

The incidence of TEAEs will be summarized by System Organ Class (SOC) and Preferred Term (PT). In addition, summaries will be provided by maximum severity (mild, moderate, severe) and by maximum relationship (related, not related) to IP. Any TEAEs leading to discontinuation of treatment or withdrawal from the study and any treatment-emergent SAEs will also be summarized, sorted by descending frequency in SOC and PT within the SAGE-324 group.

The incidence of non-TEAEs will be be summarized by SOC and PT.

Participants will be counted only once within each SOC and PT at the maximum severity in the following order: severe, moderate, and mild. Participants will be counted only once within each SOC and PT at the strongest relationship to study drug in the following order: related, not related to study drug. An AE with missing severity will be considered as 'severe', and with missing relationship to study treatment will be considered as 'related' for the purposes of summarizing these data.

The incidence of TEAEs and treatment-emergent SAEs will also be presented in order of decreasing frequency by PT.

All AEs (including those with onset or worsening before the start of IP) through the end of the study will be listed. In addition, separate listings containing individual participant AE data for all deaths, SAEs, AEs leading to treatment discontinuation, and AEs leading to study discontinuation will be provided.

8.4.2. Clinical Laboratory

All statistical analyses of laboratory values will be performed using SI units.

Some numeric lab values may be reported as '<n.n' or '>n.n'; these will be analyzed in the summary statistics as n.n/2 and n.n respectively. For example, triglycerides recorded as <0.50 mmol/L would be summarized as 0.25 mmol/L and potassium recorded as >6.0 mmol/L would be summarized as 6.0 mmol/L.

Continuous hematology (including coagulation), chemistry, and urinalysis results (raw and change from baseline) will be summarized by actual treatment group at each scheduled time point. Categorical urinalysis results will be summarized by frequencies and percentages at each scheduled timepoint. The number and percentage of participants with shift changes from baseline based on the laboratory normal ranges provided by the laboratory will be tabulated at each scheduled visit.

The number and percentage of participants with potentially clinically significant (PCS) values at any time after study drug administration (including unscheduled visits) will be summarized by treatment group for the hematology, chemistry and coagulation parameters defined in Table 9, Table 10, and Table 11, respectively.

Liver function tests will be monitored closely for potentially clinically significant values (Table 12) and will be summarized for occurrence any time post-baseline for these PCS thresholds (for conditions involving more than one parameter, the results need to be from the same timepoint).

Chemistry, hematology (including coagulation), and urinalysis data will be listed with the values outside the normal ranges flagged. Blood cell morphology and microscopy test results will be listed when available but not summarized. Pregnancy tests, and urine drugs of abuse data will be listed but not summarized.

Laboratory Parameter	Sex	Units	Criteria for PCS Val	ues (Observed values)
			High	Low
Hemoglobin	Male	g/L	>185	<115
	Female	g/L	>170	<100
Hematocrit	Male	Fraction of 1	>0.55	< 0.385
	Female	Fraction of 1	>0.49	< 0.345
Platelet count		10^9/L	>600	<125
White blood cell		10^9/L	>15	<2.5
Basophils		10^9/L	>0.5	NA
Eosinophils		10^9/L	>1.5	NA
Neutrophils		10^9/L	NA	<1.5
Lymphocytes		10^9/L	>6.0	<0.5
Monocytes		10^9/L	>1.4	NA

Table 9: Potentially Clinically Significant Values for Hematology

Laboratory Parameter	Units	Criteria for PCS Values (C	Observed values)
		High	Low
Albumin	g/L	>70	<28
Blood urea nitrogen	mmol/L	>10.71	NA
Calcium	mmol/L	>2.75	<2.0
Chloride	mmol/L	>120	<90
Creatinine	mmol/L	>3xULN or >3x Baseline	
Gamma Glutamyl Transferase		>3xULN	
Glucose	mmol/L	>13.9	<2.8
HbA1c	%	\geq 6.5% for nondiabetic patients and >8% for patients with diabetes (at screening) \geq 0.25% change from baseline	NA
Sodium	mmol/L	>150	<132
Potassium	mmol/L	>5.4	<3.3
Protein	g/L		<45
Bicarbonate	mmol/L	>34	<18
Chloride	mmol/L	>120	<90
Phosphorus	mmol/L	>1.94	<0.61
Creatine phosphokinase	U/L	>2xULN	NA
Lactate dehydrogenase	U/L	>2xULN	NA
Liver Function Tests (LFT)			
Bilirubin	µmol/L	>2xULN	NA
Aspartate Aminotransferase	U/L	>3xULN	NA
Alanine Aminotransferase	U/L	>3xULN	NA
Alkaline Phosphatase	U/L	>1.5xULN	NA

 Table 10: Potentially Clinically Significant Values for Chemistry

Table 11: Potentially Clinically Significant Values for Coagulation

Parameter	Potentially Clinically Significant Values
Prothrombin time (PT)	>=1.11 x ULN
Activated partial thromboplastin time (aPTT)	>1.5 x ULN

Parameter	Potentially Clinically Significant Values
Alanine Aminotransferase	>3xULN, >5xULN, >10xULN
Aspartate Aminotransferase	>3xULN, >5xULN, >10xULN
Alanine Aminotransferase OR	>3xULN, >5xULN, >10xULN
Aspartate Aminotransferase	
Alkaline Phosphatase	>1.5xULN, >2xULN
Total Bilirubin	>1.5xULN, >2xULN
Total Bilirubin > 2xULN AND (Alanine Aminotra	nsferase OR Aspartate Aminotransferase
>3xULN)	
Total Bilirubin >2xULN AND Alkaline Phosphata	se >2xULN AND (Alanine Aminotransferase OR
Aspartate Aminotransferase >3xULN)	
Total Bilirubin >2xULN AND Alkaline Phosphata	se <2xULN AND [(Alanine Aminotransferase

Table 12: Potentially Clinically Significant Values for Liver Function Tests

OR Aspartate Aminotransferase >3xULN) AND Alkaline Phosphatase <2xULN]

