8.4.3. Electrocardiogram

The average of multiple values collected at one visit will be used for summarization, including baseline ECG values. For each ECG measurement (heart rate and PR, QRS, QT, and QTcF intervals), the observed value at each scheduled visit and change from baseline at each scheduled visit will be provided by treatment group. This summary will also include last values on treatment and on study. Last value on treatment is defined as the last post-baseline value between first dose of IP (exclusive) and up to last dose of IP + 1 days (inclusive). Last value on study is defined as the last post-baseline value after the first dose of IP.

In addition, the number and percentage of participants with PCS and potentially clinically significant change (PCSC) values will be summarized by visit/timepoint and for any time post-baseline. Potentially clinically significant values will be identified for ECG parameters as outlined in Table 13.

A shift table of overall ECG interpretation from baseline to scheduled post-baseline visits will be presented for the following categories: 'Normal', 'Abnormal, Not Clinically Significant', and 'Abnormal, Clinically Significant'. The shift table will be presented by visit and treatment group.

Clinically significant abnormal findings will be reported as adverse events. The average of the multiple values collected at one visit of each parameter will be listed by participant.

Units	Criteria for PCS Values (Observed Values)		Criteria for PCSC Values (Change from Baseline)	
	High	Low	Increase	Decrease
msec	 >450 msec and ≤480msec >480 msec and ≤500msec >500 msec 	NA	>30 msec and ≤60 msec >60 msec	NA

 Table 13: Potentially Clinically Significant Values for QTcF

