8.4.4. Vital Signs

Vital sign results (systolic and diastolic blood pressure [mmHg], pulse pressure (mmHg), body temperature [°C], heart rate [beats per minute or bpm], and respiratory rate [breaths per minute]) and changes from baseline will be summarized by scheduled visit and treatment group. Pulse pressure is defined as [systolic blood pressure - diastolic blood pressure].

The average of multiple values collected at one visit will be used for summarization, including the Day 1 triplicates assessments of supine and standing blood pressure and heart rate.

Potentially clinically significant values will be identified for vital sign parameters as outlined in Table 14. For any post-baseline visit, potentially clinically significant values will be summarized by treatment group and visit.

The number and percentage of participants with orthostatic hypotension, defined as either a decrease in systolic blood pressure of ≥ 20 mmHg or a decrease in diastolic blood pressure of ≥ 10 mmHg from supine to standing position, will be summarized by treatment group at each visit. The PCS and orthostatic hypotension at baseline will be evaluated using the average of 3 triplicates.

Vital sign results will be listed by participant and timing of collection.

Any vital sign results considered clinically significant by the investigator will be captured as adverse events.

Vital Sign	Units	Criteria for PCS (Observed values)	Values)	Criteria f values (C Baseline	for PCSC hange from values)
		High	Low	Increase	Decrease
Heart rate (supine and standing)	Beats/min	>120	<40		
Systolic Blood Pressure (supine and standing)	mmHg	>180	<90	≥30	≥30
Diastolic Blood pressure (supine and standing)	mmHg	>110	<50	≥20	≥20
Supine - Standing Systolic Blood Pressure	mmHg	≥20			
Supine – Standing Diastolic Blood Pressure	mmHg	≥10			
Orthostatic hypotension: supine – standing SBP and	mmHg	$SBP \ge 20 \text{ and} \\ DBP \ge 10$			
DBP		$\begin{array}{c} \text{SBP} \geq 20 \text{ or } \text{DBP} \\ \geq 10 \end{array}$			

Table 14: Potentially Clinically Significant Values for Vital Sign Parameters

Sage Therapeutics, Inc. CONFIDENTIAL

8.4.5. **Physical Examination**

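### Lab PCS counts in SAP 8.4.2 do not separate values already past the threshold at baseline from new ones

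*SAP*

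**What the plan says.** **Laboratory (SAP 8.4.2).** For hematology, chemistry and coagulation, the plan reports by treatment group the number and percentage of "participants with potentially clinically significant (PCS) values at any time after study drug administration (including unscheduled visits". Liver tests "will be summarized for occurrence any time post-baseline for these PCS thresholds". The criteria are in Tables 9 to 12. They are absolute values or multiples of the upper limit of normal, with two exceptions in Table 10: creatinine has an alternative limb relative to baseline, and the HbA1c cell includes a change from baseline. Shift tables are also planned, based on the laboratory's normal ranges and tabulated by scheduled visit, together with change-from-baseline summaries.

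**QTcF (SAP 8.4.3, Table 13).** The number and percentage of participants with "PCS and potentially clinically significant change (PCSC) values will be summarized by visit/timepoint and for any time post-baseline". The bands fall under "Criteria for PCS Values (Observed Values"), and a separate set of PCSC categories covers increases from baseline of more than 30 and more than 60 msec.

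**Vital signs (SAP 8.4.4).** "The PCS and orthostatic hypotension at baseline will be evaluated using the average of 3 triplicates". The section does not say that post-baseline counts are conditioned on that evaluation.

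**Related definitions.** SAP 8.1 defines baseline as the last nonmissing predose measurement. SAP 8.4.1 counts an adverse event as treatment-emergent only if it starts or worsens at or after the start of IP. SAP 8.4 states that no hypothesis tests will be done on safety data.

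**The concern.** A PCS table by arm is normally read as what happened on treatment. Here a value that was past the cut-off before the first dose and stays there is added to the values that crossed it afterwards, and the table gives no means of telling them apart. The adverse event tables apply an onset-or-worsening rule; the lab PCS tables do not.

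With no tests planned and about 26 to 40 participants per arm, readers will compare small raw counts across placebo, 15, 30 and 60 mg. One or two carried-over participants in a single arm could look like the start of a dose trend, or could blur a real one.

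**Working it through.** The plan states no figure on this point, so there is none to reproduce. The check is a comparison of the text, then an illustration under stated assumptions.

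**Step 1. Is there a baseline condition anywhere?** Nothing visible in SAP 8.1, 8.4, 8.4.2 or 8.4.3, or in Protocol 13.6.2, limits the numerator or denominator to participants below the PCS threshold at baseline, requires worsening, or calls for a PCS-threshold shift. The creatinine limb relative to baseline is joined by *or*, so a participant already above 3 x ULN still counts.

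**Step 2. Do the shift tables fill the gap?** Take two participants whose platelets are below the normal range at baseline. One was already below 125 x 10^9/L and stays there. The other was above 125 and falls below it on treatment. On normal ranges both go from low to low, so neither shows a shift, and both count once in the PCS table. The new case and the carried-over case look identical in both displays.

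**Step 3. How large could the effect be?**

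Inputs:
- Monotherapy arm: 26 (SAP 5.2). Adjunct arm: up to 14 (SAP 5.2). Overall: 26 + 14 = 40 per arm, and 40 x 4 = 160, as planned.
- Baseline prevalence p of a given PCS criterion: **assumed** 1%, 2%, 5% and 10%.
- Persistence s (the chance that a baseline-PCS participant has at least one post-dose PCS value): **assumed** 50% or 100%.

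Carried-over participants per arm: X ~ Binomial(n, q), with q = p x s and mean nq. For two independent arms, P(|X1 - X2| >= 2) is the sum of P(X1 = i) P(X2 = j) over all pairs with |i - j| >= 2.

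Worked case, n = 26, q = 0.01: P(0) = 0.770, P(1) = 0.202, P(>=2) = 0.028, P(>=3) = 0.002. Leading terms: 2 x (0.770 x 0.028 + 0.202 x 0.002) = 0.044.

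| p | nq, s=100% (n=26 / n=40) | P(diff >= 2), s=100% (n=26 / n=40) | P(diff >= 2), s=50% (n=26 / n=40) |
|---|---|---|---|
| 1% | 0.26 / 0.40 | 0.044 / 0.085 | 0.013 / 0.028 |
| 2% | 0.52 / 0.80 | 0.122 / 0.205 | 0.044 / 0.085 |
| 5% | 1.30 / 2.00 | 0.318 / 0.427 | 0.161 / 0.257 |
| 10% | 2.60 / 4.00 | 0.479 / 0.571 | 0.318 / 0.427 |

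These are for one criterion and one given pair of arms.

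**Step 4. Share of the reported count.** Assume a true new-onset rate of 2%, so that new cases number n(1 - p) x 0.02. At n = 40 and s = 100%, p = 1% gives 0.40 / (0.40 + 0.79) = 34% carried over, and p = 10% gives 4.00 / (4.00 + 0.72) = 85%. At s = 50% the two shares are 20% and 74%.

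**Step 5. Is high persistence plausible?** Labs are scheduled at eight post-dose visits (Days 8, 15, 29, 43, 57, 71, 91 and 104), and one exceedance is enough. If a baseline-PCS participant exceeded independently with probability 30% at each visit, the chance of being counted would be 1 - 0.7^8 = 94%. Correlation between visits, early discontinuation, or an analyte sampled less often would lower it.

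**The case against.** Several points on the other side stand.

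- **No between-arm bias.** A reader might infer that the rule tilts the comparison against SAGE-324. It does not: placebo is counted identically and baseline status is balanced by randomization in expectation. The plan does not call these counts treatment-emergent.
- **Not the sole safety evidence.** It would be too strong to treat the PCS tables as the plan's main lab or QTcF signal. Change-from-baseline summaries, normal-range shifts, full listings and the adverse event tables are all planned, and Protocol 12.2.1 turns clinically significant abnormalities into adverse events.
- **QTcF is largely covered.** The PCSC categories separate change from level, and change from baseline is summarized by visit. The ECG windows in SAP Table 6 include Day 1, so the by-visit PCS display may show baseline status too.
- **HbA1c is not a safe example.** A diabetic participant whose HbA1c stays above 8% while falling may seem the obvious case. The same Table 10 cell adds a change of at least 0.25% from baseline, and the available text shows no connective. If an increase is also required, that participant is not counted.
- **Prevalence may be low.** Inclusion criterion 3 requires no clinically significant ECG or laboratory findings in the investigator's judgement, and exclusion criterion 7 removes active significant disease. Neither applies the PCS cut-offs. The public exclusion list passes from 14 to 16, so one cannot say that no numeric limit exists. Many criteria, such as ALT above 10 x ULN, will rarely be met at baseline.
- **Excluding baseline-PCS participants has a safety cost.** For a single-threshold criterion it would remove from the table someone who starts past the cut-off and worsens sharply on treatment.

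None of this supplies the missing separation for the lab criteria. It does limit the size of the point and determine the form of the remedy.

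**Conclusion.** The point holds for the laboratory criteria and is minor. As written, SAP 8.4.2 pools carried-over and new PCS values, and no other planned lab table separates them. The consequence is inflated rates and extra chance imbalance in descriptive tables.

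Its size cannot be derived from the documents, because they give no baseline PCS rate. On an assumed 1-10% prevalence with full persistence, the chance of a difference of 2 or more carried-over participants between two given arms is 4-48% at n = 26 and 9-57% at n = 40. At 50% persistence it is 1-32% and 3-43%. For rare criteria the effect is close to nil; it matters for cut-offs near the normal limit, such as prothrombin time at 1.11 x ULN.

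The documents do not support extending this to a systematic bias between arms, or to a comparable gap for QTcF.

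**What to change.** Keep the any-post-dose PCS counts as planned. In SAP 8.4.2 add, for each lab criterion and by arm, a table of baseline PCS status by worst post-baseline PCS status, including unscheduled values. From it report:

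1. the new-onset count, with participants not PCS at baseline and having at least one post-baseline value as denominator;
2. separately, participants PCS at baseline, with baseline and worst post-baseline values so that any worsening stays visible.

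For creatinine and HbA1c, state that baseline status uses the absolute limb only, and spell out how the limbs combine. The same table for the QTcF bands in 8.4.3 is optional.

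The cost is a short addition to the SAP, one derived baseline flag from data already collected, extra table rows, and denominators that differ by parameter. No data are dropped and the listings are unchanged.

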^b Complete physical examinations and a comprehensive neurological examination, including MSEs, should be performed at Screening and EOT and as clinically necessary (see Section 12.1.3). Targeted physical and neurological examinations should be performed at other times as indicated by AEs.

^c On Day 1, supine and standing blood pressure and heart rate will be collected in triplicate at least 15 minutes apart, measured after the participant has been in the supine position for at least 5 minutes and then repeated 1 minute and 3 minutes after standing. Respiratory rate and temperature are collected once on Day 1.

^d ECGs will be collected and read centrally. All ECGs must be performed after the participant has been in a supine position for at least 5 minutes.

^e Chemistry, hematology, coagulation, and urinalysis to be collected at all timepoints except Day 97. Note: Myoglobin (urinalysis) and serum creatine kinase (biochemistry) will be collected at Screening. In addition, myoglobin (urinalysis) and serum creatine kinase (biochemistry) may be collected at any additional timepoints at the discretion of the investigator (including Day 97). A serum sample for blood alcohol level will be collected at all timepoints (including Day 97). HbA1c will be collected at Screening and EOS/ETV Visit only.

^g A videographer will record TETRAS administration at Screening.

^h Washout of prestudy ET drug(s) except propranolol after the ICF was signed (Section 9.2.2.1) must be completed prior to Screening TETRAS assessment.

ⁱ Participants will be trained by study personnel on the use of software applications, IP diary, and devices necessary for the conduct of the study.

^j Will be administered once daily, to be taken before bed, with a snack if bedtime is not within 2 hours of the evening meal. The 60-mg dose group will receive 15 mg SAGE-324 from Day 1 to Day 14, then 30 mg from Day 15 to Day 28, then 45 mg from Day 29 to Day 42, and then 60 mg from Day 43 to Day 90.

^k A phone call to follow up on any AE(s) will be conducted, if deemed appropriate by the investigator, to review the current status of the participant.

¹ Including all medications and supplements taken within the 30 days prior to signing the ICF through the first dose of IP, as well as a complete history of all treatments for ET since the year of diagnosis.

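### The combined liver criteria in SAP Table 12 count only within one timepoint, and no visible planned table links a participant's crossings at different visits

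*SAP*

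**What the plan says.** SAP 8.4.2 (Clinical Laboratory) sends liver results to Table 12, titled "Potentially Clinically Significant Values for Liver Function Tests". It says that they "will be summarized for occurrence any time post-baseline for these PCS thresholds", and then adds the restriction "for conditions involving more than one parameter, the results need to be from the same timepoint".

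Table 12 holds two kinds of row:

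- **Single-parameter rows.** ALT, AST, and ALT or AST are each counted at ">3xULN, >5xULN, >10xULN". Alkaline phosphatase and total bilirubin are each counted at ">1.5xULN, >2xULN".
- **Combined rows.** There are three. The first is total bilirubin above 2xULN together with ALT or AST above 3xULN. The other two add alkaline phosphatase above 2xULN or below 2xULN.

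On sampling, a footnote to the schedule of assessments in the protocol synopsis states: "Chemistry, hematology, coagulation, and urinalysis to be collected at all timepoints except Day 97". The visible list of displays in SAP Appendix D has one liver table (14.3.4.1.4) and one clinical chemistry listing (16.2.8.1.1).

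**The concern.** The single-parameter rows ask whether a participant ever crossed a threshold after baseline. The combined rows ask whether the participant crossed two or three thresholds at once. If a bilirubin rise follows a transaminase peak, or comes before it, the crossings can fall at different visits. The combined rows then show nothing.

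Linking the two abnormalities to one person is the purpose of a combined row. Separate single-analyte counts cannot do that. What is at stake is the reported number of participants with both abnormalities. In a study of this size that number would be small, so one participant more or less would be noticed.

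**Working it through.** The plan gives no figure to reproduce. The check applies the counting rule to the sampling schedule.

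**1. Sampling gaps.** The schedule of assessments (protocol Table 2, SAP Appendix A) places post-baseline chemistry on Days 8, 15, 29, 43, 57, 71, 91 and 104. The differences between target days are:

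- 15 − 8 = 7
- 29 − 15 = 14
- 43 − 29 = 14
- 57 − 43 = 14
- 71 − 57 = 14
- 91 − 71 = 20
- 104 − 91 = 13

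Scheduled draws are thus 7 to 20 days apart on target days. Visit tolerances and unscheduled draws can shift individual gaps.

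**2. The rule applied to one participant.** The values below are hypothetical, chosen only to exercise the rule.

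| Visit | ALT (xULN) | Bilirubin (xULN) | ALT >3 | Bilirubin >2 | Both |
|---|---|---|---|---|---|
| Day 43 | 4.0 | 1.2 | yes | no | no |
| Day 57 | 2.5 | 2.5 | no | yes | no |

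Neither visit meets the first combined row. The other two combined rows contain that condition and add one on alkaline phosphatase, so they fail whatever the alkaline phosphatase value is. The count is 0 on all three.

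Using the highest post-baseline values instead gives ALT 4.0 and bilirubin 2.5. Both thresholds are met, and the count is 1.

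**3. Does the meaning of timepoint matter?** The SAP does not say whether it means one sample or one analysis visit. Days 43 and 57 are different scheduled visits, and SAP 8.3.2, which 8.4 carries over to safety summaries, keeps scheduled visits at their nominal value. The example scores 0 on either reading. The two readings can differ for an unscheduled repeat, because the laboratory windows in SAP Table 7 are wide (Day 91, for example, covers Days 82 to 96, which is 96 − 82 + 1 = 15 days).

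**4. What the single-analyte rows reveal.** The example participant adds 1 to the ALT >3xULN row, 1 to the ALT or AST >3xULN row and 1 to the bilirubin >2xULN row. Suppose that, in an arm of n, a participants are in the ALT or AST row and b are in the bilirubin row. The number in both lies between max(0, a + b − n) and min(a, b). For a = b = 1 and n = 160 / 4 = 40, that is from max(0, −38) = 0 to min(1, 1) = 1. The table looks the same whether the crossings belong to one person or to two.

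**5. Size of one case.** With planned numbers, one participant is 1/40 = 2.5% of an arm overall, 1/26 = 3.8% of a monotherapy arm and 1/14 = 7.1% of an adjunct arm. The documents give no rate for crossings at different visits, so no expected count can be derived.

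**The case against.** The strongest reply is that this is a prespecified choice and not an error. Requiring concurrent values favors specificity: it avoids joining a transaminase rise and an unrelated bilirubin rise weeks apart. Nothing else in the protocol or SAP contradicts the rule. That stands, and it is the reason for keeping the same-timepoint rows.

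Three stronger readings are tempting, and the documents do not support them.

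- **That the case is lost from safety reporting.** It is not. The participant counts in the single-analyte rows, and SAP 8.4.2 lists chemistry by participant with out-of-range values flagged. Protocol 12.1 has the investigator judge each abnormal result for clinical significance. Under protocol 12.2.1, clinically significant results, and those leading to discontinuation, interruption or treatment, are adverse events. The gap is in the summary tables.
- **That both values must come from one blood draw, so any partial unscheduled repeat is missed.** The SAP says timepoint and leaves it undefined. Under an analysis-visit reading, a repeat might share a timepoint with the scheduled draw.
- **That one uncounted participant would change the safety conclusion.** SAP 8.4 plans no hypothesis tests on safety data, and no decision rule in the documents depends on the Table 12 counts. One case would change a reported number; whether it would change a conclusion cannot be said.

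A fixed pairing window, such as a set number of days for bilirubin to follow ALT or AST, is also open to objection. The documents give no such window, and a one-directional rule would still miss bilirubin crossing first.

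**Conclusion.** The point holds as a limitation of a descriptive summary. As written, crossings at different scheduled visits score 0 on all three combined rows, and no visible planned table shows that they belong to one participant. This follows from the counting rule and the sampling schedule, and from no assumption about the drug.

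Two limits apply. Parts of the SAP, including its list of displays, are blacked out, so the statement about planned tables covers only what can be seen. The frequency of the pattern is unknown: the example shows that the rule can miss it, not that it will occur.

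The primary and secondary efficacy analyses, the estimand and the sample size are unaffected. This is a low-priority but inexpensive improvement.

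**What to change.** Keep the three same-timepoint rows. Add one row to Table 12 and to Table 14.3.4.1.4 that counts participants with total bilirubin above 2xULN and ALT or AST above 3xULN, each at any time post-baseline, in either order, including unscheduled visits. By construction this count is at least as large as that of the first same-timepoint row, and the difference is the number of participants who met the two thresholds only at different timepoints.

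Add a listing of every participant who meets either rule, with dates and the ALT, AST, bilirubin and alkaline phosphatase values. Showing alkaline phosphatase there avoids an arbitrary choice of which date's value to use in a cross-visit row. The SAP should also say whether timepoint means one sample or one analysis visit, so that the retained rows are reproducible. If the sponsor prefers a pairing window narrower than the whole post-baseline period, its length is the sponsor's choice and should be stated in advance.

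The cost is a short SAP edit, one derived flag and one listing. No new data are needed. The downside is that a few unrelated pairs may need medical review.
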